9.2 Infected Cells Antibody Binding Assay (ICABA)

The ICABA assay is conducted to address the exploratory objective to evaluate immunogenicity of the vaccine regimens. ICABA will test for the presence of antibodies binding to the surface of HIV-1 infected cells in the serum of infant participants using Infectious Molecular Clone (IMC)-infected target cells. To quantify maternal immune responses, paired mothers' sera from corresponding visits also tested, even though the mothers do not receive any study product.

CEM.CCR5.NKR cells infected with HIV-1 IMC CH0505, and mock-infected cells are tested in a 96-well plate for the ICABA. Participant sera in addition to controls are incubated with the IMC-infected cells and the presence of bound antibodies is detected on the surface of the cells using flow cytometry.

ICABA assays are performed on infant participant serum samples collected at visit 1 (cord blood), visit 2 (whole blood), and visit 12 (whole blood). For the analysis, visit 2 is considered as "primary baseline", and visit 1 as an "exploratory baseline". The primary plots and tables will not include visit 1, only visit 2 and 12. Paired maternal serum samples at visits 2 and 12 are also assayed to assess maternal immune response.

As the study participants (infants) are HIV-exposed, the infant baseline responses are expected to be higher than usual due the influence of the maternal immune system. For this reason, visit 2 primary baseline values are not used in response calls, and an assay specific fixed positivity threshold (provided by the lab) will be used instead.

The data from ICABA are quantitative, measuring the Mock Background Subtracted %IgG. Responses are measured for IgG. The paired maternal immune responses are also tabulated and plotted for comparison, but not included in primary analysis. There is no baseline subtraction applied to the responses, and to make response calls a fixed positivity threshold is applied to background (plate-level assay background) subtracted response magnitudes. A positive response is defined as Mock Background Subtracted %IgG >= 5%.

9.2.1 List of Tables

- Infant ICABA response rate by treatment group, study visit (v2 and v12)
- Distribution of ICABA response magnitude among all infant participants by treatment group, study visit (v2 and v12)
- Distribution of ICABA response magnitude among infant positive responders only by treatment group, study visit (v2 and v12)
- Distribution of AUC among all infant participants by treatment group, study visit (v2 and v12),
- Distribution of AUC among infant positive responders only by treatment group, study visit (v2 and v12)

9.2.2 List of Graphs

- Barcharts of infant response rates and boxplots of response magnitudes by treatment group, study visit (v2 and v12), and antigen
- Exploratory figures [all figures include both positive and negative responders. All figures are implemented for all vaccine groups combined, and for all placebo groups combined]
 - Scatterplot of infant response magnitude at v1 vs v2 [this plot helps to justify and inform the use of v1 responses as a substitute for missing v2 responses]

- Scatterplot of infant response magnitude vs maternal response magnitude at each study visit (v2 and v12) [this plot informs on whether maternal immune responses are associated with infant immune responses, and potentially informative for isolating vaccine-induced immune responses]
- Side by side boxplot of infant response magnitude and maternal response magnitude at each visit (v2 and v12), with mother-infant pairs connected across the side-by-side boxplot [this plot is an alternative way of visualizing the mother-infant association shown in the last plot]
- Side by side boxplot of maternal minus infant response magnitude by visit (v2 and v12) [this plot shows the distribution of the difference in maternal and infant immune responses, i.e. a specific contrast of the two immune responses]
- Side by side boxplot of infant v12 minus v2 response magnitude and maternal v12 minus v2 response magnitude, with mother-infant pairs connected across the side-by-side boxplot [this plot examines whether infant change in immune response is associated with maternal immune response change]

9.3 Binding Antibody Multiplex Assay (BAMA)

The BAMA analysis corresponds to the primary endpoint to assess magnitude of HIV-1 Env gp120, CD4 binding site and V1V2-specifc serum IgG binding antibodies, as assessed by BAMA 2-weeks post 5th vaccination. The following protocol objectives and endpoints will be assessed using customized BAMA:

Primary endpoints 2: Magnitude of HIV-1 Env gp120, CD4 binding site and V1V2-specific serum IgG binding antibodies, as assessed by BAMA two weeks after the 5th vaccination

Secondary Objective 3: To measure Fc-mediated antibody effector functions

Secondary Endpoint 3: Response rate and magnitude of vaccine elicited serum binding antibodies to FcR proteins, as assessed by BAMA 2 weeks post 5th vaccination

Exploratory Objective 3: To evaluate effects of maternal antibody in cord blood, serum/plasma, and breast milk on the humoral response of infants.

The customized HIV-1 BAMA employs flow cytometry-based technology that utilizes antibody and antigen interactions to test for the presence of specific antibodies in an unknown sample with the added advantage of multiplexing the antigens of interest [6,7,8]. The partially purified HIV antigens are covalently coupled to specific fluorescent bead sets. Bead sets coupled to antigens of interest are mixed to allow for multiplexing and samples added to the beads. This step is followed by the addition of a secondary anti-human antibody conjugated to biotin and/or phycoerythrin (PE) to allow for a fluorescent readout of secondary antibody binding. Microspheres are read on either a Bioplex 200 or Luminex Flexmap 3D instrument to measure Fluorescence Intensity (FI).

FcR BAMA: FcR BAMA utilized Fc Receptor (FcR) proteins tetramerized with phycoerythrin (PE) as a detection reagent to determine antigen specific binding antibody interactions with FcRs. Microspheres are read on a Flexmap 3D instrument.

The following immune response magnitude definitions are considered for this assay:

- i. Net binding Mean Fluorescence Intensity (Net MFI) Mean fluorescence intensity for the antigen wells minus the MFI for the blank well on the assay plate (Definition 1)
- ii. Titration (EC50/Area Under the Curve, AUC): If high binding is observed and it's deemed scientifically important, samples may be titrated to calculate antibody titers (Definition 2)

Both response magnitudes will be plotted and analyzed on a log scale. Both Definition 1 and Definition 2 are measured post-fifth vaccination. Definition 1 will be measured at baseline, while Definition 2 will also be measured at baseline for most IgG antigens except CH505TF.6R.SOSIP.664.v4.1_avi.2-Bio/293F, gp70_CH505TF_V1V2_avi/293F, and gp70_CH505TF_V1V2_N156KN160K_avi/293F. FcR data will be run at a single dilution (1:50) and therefore Definition 1 will be employed.

Primary antigens for analysis, with 'match' or 'mismatch' status with respect to the study vaccine, are as shown. Antigens considered 'wild type' vs. 'mutant type' are designated as such:

CH0505_CON D7gp120_avi/293/Mon	Matched	Wild type
CH0505_CON D7gp120_D368R_avi/293/Mon	Matched	Mutant type
CH505TF D7gp120d371_avi/293/Mon	Matched	Mutant type
CH505TFD8N156KN160K_avi/293i Mon	Matched	
CH505TF.6R.SOSIP.664.v4.1_avi.2-Bio/293F	Matched	
Con 6 gp120/B	Mismatched	
Con S gp140 CFI	Mismatched	
1086C_D7gp120.avi/293F	Mismatched	
gp41	Mismatched	
gp70_CH505TF_V1V2_avi/293F	Matched	
gp70_CH505TF_V1V2_N156KN160K_avi/293F	Mismatched	

Infant participant serum samples are assayed at visit 1 (cord blood), visit 2 (whole blood), and visit 12 (whole blood). For the analysis, visit 2 is considered as the preferred baseline, and when not available visit 1 will be used; we refer to this as 'v1/2'. Paired maternal serum samples at visits 2 and 12 are also assayed to assess maternal immune response.

As the study participants (infants) are HIV-exposed, the infant baseline responses are expected to be higher than usual due the influence of the maternal immune system. For this reason, visit 1/2 baseline values are not used in response calls. HVTN 115 Part A baseline data will be used as statistical baseline to determine the antigen specific positivity thresholds for HVTN 135, for the antigen(s) have the same detection and conjugate (dilution 1:50 and Isotype-Conjugate (ex. IgG-PE)) in the two studies.

Infant samples are declared to have a positive response if they meet the following three conditions:

- 1. net MFI values >= antigen specific cutoff values (max(95th percentile of statistical baseline, 100 net MFI))
- 2. net MFI values > 3x antigen specific median HVTN 115 baseline net MFI values
- 3. MFI values > 3x antigen specific median HVTN 115 baseline MFI values

The differential binding response is measured by the ratio of magnitude of response (net MFI) to wild type vs mutant type antigens. A differential binding response is considered to be positive when it meets the three criteria above, plus three additional criteria at screening dilution or selected dilution (when samples are titrated):

- 4. MFI ratio (wild type/mutant type) ≥ 2.5
- 5. net MFI ratio (wild type/mutant type) ≥ 2.5
- 6. wild type antigens' MFI and net MFI ≥ 250

Epitope binding percentages for the set of CD4-bs analytes are calculated when wild type's differential binding response is positive as (Wildtype net MFI - Mutant net MFI)/Wildtype net MFI \times 100 at the selected dilution where most of both Wild Type and Mutant Type analytes' net MFI fall in the assay linear range [100, 22000] net MFI at a time point.

9.3.1 List of Tables

- Summary table of BAMA response rate for infant participants by treatment group, study visit (v1/2 and v12), and antigen
- Summary statistics of Net MFI among all infant participants by treatment group, study visit (v1/2 and v12) and antigen
- Summary statistics of Net MFI among infant positive responders only by treatment group, study visit (v1/2 and v12), and antigen
- Summary statistics of BAMA AUC among all infant participants by treatment group, study visit (v12), and antigen
- Summary statistics of BAMA AUC among infant positive responders only by treatment group, study visit (v12), and antigen
- Summary statistics of differential binding among all infant participants by treatment group, study visit (v1/2 and v12) and antigen

9.3.2 List of Figures

- Bar plots of infant BAMA response rates and boxplots of Net MFI and AUC response magnitudes by treatment group, study visit (v1/2 and v12), and antigen [When both net MFI and AUC data are available, first show AUC data plots then net MFI plots]
- Bar and box plots show infant differential binding response rates and the distribution of differential binding response rates by antigen, visit, and treatment group

- Scatter plot of infant wild type vs. mutant binding response by antigen, visit, and treatment group
- Exploratory figures: [all figures include both positive and negative responders and are implemented for both magnitude definitions, when possible. All figures are implemented for all vaccine groups combined, and for all placebo groups combined]
 - O Scatterplot of infant response magnitude at v1 vs. v2 by antigen [this plot helps to justify and inform the use of v1 responses as a substitute for missing v2 responses]
 - Scatterplot of infant response magnitude vs. maternal response magnitude at v1/2 by antigen [this plot informs on whether maternal immune responses are associated with infant immune responses, and potentially informative for isolating vaccine-induced immune responses]
 - Scatterplot of infant response magnitude at v1/2 vs v12 by antigen [this plot informs on whether passively-acquired immune responses are associated with active immune responses, and potentially informative for isolating vaccine-induced immune responses]
 - Scatterplot of infant vs. maternal differential binding at v1/2 by antigen
 - Side by side boxplot of infant response magnitude and maternal response magnitude at each visit (v1/2 and v12) by antigen, with mother-infant pairs connected across the sideby-side boxplot [this plot is an alternative way of visualizing the mother-infant association]
 - Side by side boxplot of infant differential binding response and maternal differential binding response at each visit (v1/2 and v12) by antigen, with mother-infant pairs connected across the side-by-side boxplot
 - O Boxplot of infant v12 minus v1/2 response magnitude (fold change) by antigen [this plots a change in antibody post-baseline]
 - Scatterplot of infant response magnitude vs. infant gp41 response magnitude by visit (v1/2 and v12) and antigen [this plot explores the utility of gp41 responses as a marker of maternally-acquired antibody]
 - Boxplot of infant response magnitude to a given antigen minus infant response magnitude to gp41, by visit (v1/2 and v12) and antigen [this plots a specific contrast in gp41 and vaccine-induced antibody]

9.4 Antibody Dependent Cellular Phagocytosis (ADCP)

ADCP assay is conducted to assess the ability of polyclonal IgG, from participant serum samples, to mediate phagocytosis. The ADCP analysis corresponds to the secondary endpoint to assess the response rate and magnitude of serum antibody-dependent cellular phagocytosis (ADCP), as assessed by flow cytometry 2 weeks post 5th vaccination.

ADCP assay is a qualified assay employing flow cytrometric-based technology that measures the ability of antibodies to mediate phagocytosis. Biotinylated antigen conjugated to neutravidin beads are incubated with patient serum or plasma, purified IgG, or monoclonal antibodies. A monocyte cell line (THP-1) is added to the immune complexes and spinoculated at 4°C followed by incubation at 37°C. Cells are then analyzed for bead internalization by flow cytometry (bead positive versus bead negative detection). The primary antigen for analysis is CH505TF D7gp120.avi/293F. Additional antigens may be assessed on an exploratory level.

A phagocytic score is determined based on the ratio of experimental sample to PBS control. Mean phagocytosis score is defined as: (% bead positive for participant x MFI bead positive for participant) / (% bead positive for PBS only control x MFI bead positive for PBS only control).

38 infant participant serum samples are assayed at visit 1 (cord blood), visit 2 (whole blood), and visit 12 (whole blood). For the analysis, visit 2 is considered as the preferred baseline, and when not available visit 1 will be used; we refer to this as 'v1/2'. Paired maternal serum samples at timepoint(s) visit 2 and visit 12 may also be assayed.

As the study participants (infants) are HIV-exposed, the infant baseline responses are expected to be higher than usual due the influence of the maternal immune system. For this reason, primary baseline values are not used in response calls. HVTN 115 baseline data will be used as statistical baseline to determine the antigen specific positivity thresholds for HVTN 135.

Positivity calls will be based on two criteria:

- 1. Average ADCP score >= antigen specific cutoff values (max(95th percentile of statistical baseline, 1))
- 2. Average ADCP score > 3x antigen specific median 115 baseline average ADCP score

9.4.1 List of Tables

- Summary table of ADCP response rates for infants by treatment group, study visit (v1/2 and v12), and antigen
- Summary statistics of average phagocytosis score among all infant participants by treatment group, study visit (v1/2 and v12), and antigen
- Summary statistics of average phagocytosis score among infant positive responders only by treatment group, study visit (v1/2 and v12), and antigen

9.4.2 List of Figures

- Bar plots of infant ADCP response rates and boxplots of average phagocytosis score by treatment group, study visit (v1/2 and v12), and antigen
- Exploratory figures [all figures include both positive and negative responders. All figures are implemented for all vaccine groups combined, and for all placebo groups combined]
 - Scatterplot of infant response magnitude vs. maternal response magnitude at each study visit (v1/2 and v12) by antigen [this plot informs on whether maternal immune responses are associated with infant immune responses, and potentially informative for isolating vaccine-induced immune responses]
 - Side by side boxplot of infant response magnitude and maternal response magnitude at each visit (v1/2 and v12) by antigen, with mother-infant pairs connected across the sideby-side boxplot [this plot is an alternative way of visualizing the mother-infant association shown in the last plot]
 - O Side by side boxplot of maternal minus infant response magnitude by visit (v1/2 and v12) and antigen [this plot shows the distribution of the difference in maternal and infant immune responses, i.e., a specific contrast of the two immune responses]
 - O Side by side boxplot of infant v12 minus v1/2 response magnitude and maternal v12 minus v2 response magnitude by antigen, with mother-infant pairs connected across the side-by-side boxplot [this plot examines whether infant change in immune response is associated with maternal immune response change]

9.5 Env-specific B-cell Phenotyping (BCP)

The Env-Specific B cell Phenotyping (BCP) assay will be used to identify and characterize HIV-1 Env-specific B cells and plasmablasts induced by vaccination. The BCP analysis corresponds to

the primary objective to determine whether vaccination with CH505TF gp120 adjuvanted with GLA-SE initiates B-cell lineages potentially capable of generating a broadly neutralizing antibody response. HVTN135 study design will also allow for the comparison infant and adult immune responses to CH505TF gp120 as it mimics the design of HVTN115 that evaluated CH505TF gp120 in adult humans. The study will evaluate two dose levels of the vaccine (20 and 5 mcg) and two dose levels of the adjuvant (2.5 and 5 mcg) given at five time points over 54 weeks. The study consists of 38 total participants: 28 vaccinees and 10 placebo recipients. All vaccines as well as the placebo will be delivered via intramuscular injection (IM).

Samples from baseline (Obtained from cord blood), visit 8 and visit 12 from the maximum of 38 infants in the protocol will be assayed as part of this study.

HIV-1 Env-specific B cells induced by vaccination were identified and characterized using fluorescently-labeled recombinant Env proteins in the context of a flow cytometry panel to identify and characterize those B cells.

Total B cells are identified using doublet exclusion, lymphocyte scatter profile, a viability dye to exclude dead cells, and are negative for lineage markers: CD3, CD56 and CD14; and positive for CD19 and CD20. B cells are further gated as IgD-, then IgG+, and IgA+.

Data from Low IgD- B cells (<5000) and assay results deemed unreliable for analysis by the lab were excluded from the analysis.

To assess positivity for the detection of IgD-, IgG+, and IgA+ B cells, the 85th percentile of the proportion of cells in the subset was calculated, among all placebo recipients (C2+C4+C6+C8) for a given cell subset and visit (visits 8 and 12) and used as the threshold for defining a positive response. Positivity was not assessed for visit 1.

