6.1.2 Sample size calculations for immunogenicity

To address binding antibody endpoints, the analysis will descriptively summarize binding response positivity call rates to test superiority of IgG binding Ab responses for CH103-like CD4bs and V1V2 for comparisons versus zero using binomial exact tests with 5% type-I error rate each. Note that if in HIV-infected women, maternal antibodies that differentially bind to the CD4bs occur at a rate of 51% [estimated from n = 14 CAPRISA 002 women infected 2-3 years (76) and are transmitted to the infants, comparisons at early timepoints may be confounded by background positivity. Therefore, we have chosen the 2 weeks post 5th vaccination timepoint (~ one year) for the power calculation. By this time, both transplacental and breastmilk-associated antibodies (breast-feeding typically ceases at 6 months of age in the South Africa setting) are expected to have waned to below detectable levels, obviating the requirement to increase the placebo recipient sample size for a comparison with this high background rate. The following calculations assume a 25% rate of missing data to accommodate missingness at the 1-year timepoint.

The main goals of this trial regarding immunogenicity outcomes involve a preliminary estimation of rates of "response" (defined for Primary Endpoint 2 as initiation of either the CD4bs or the V1V2 B cell lineage) based on data from immune assays among vaccinees. No adjustment for multiple comparisons will be

made for the use of multiple assays. The precision with which the true response rate can be estimated from the observed data depends on the true underlying response rate and the sample size. Two-sided 95% confidence intervals for the response rate based on observing a rate of responses in the vaccinees is shown in Table 6-3. Calculations are done using the score test method (75). The n=13 assumes a 25% rate of missing immunogenicity data.

Table 6-3 Two-sided 95% confidence intervals for the true response rate based on observing a particular rate of responses in the vaccinees (n = 13)

No. of responses	Observed response rate (%)	95% Confidence interval
1/13	7.7	[1.4, 33.3]
2/13	15.4	[4.3, 42.2]
3/13	23.1	[8.2, 50.3]
4/13	30.8	[12.7, 57.6]
5/13	38.5	[17.7, 64.5]
6/13	46.2	[23.2, 70.9]
7/13	53.8	[29.1, 76.8]
8/13	61.5	[35.5, 82.3]
9/13	69.2	[42.4, 87.3]
10/13	76.9	[49.7, 91.8]
11/13	84.6	[57.8, 95.7]
12/13	92.3	[66.7, 98.6]
13/13	100	[77.2, 100]

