8.4 Immunogenicity analysis

8.4.1 General Approach

For the statistical analysis of immunogenicity endpoints, data from enrolled participants will be used according to the initial randomization assignment regardless of how many injections they received. Additional analyses may be performed, limited to participants who received all scheduled injections per protocol. Assay results that are unreliable, from specimens collected outside of the visit window, or from HIV-infected participants post-infection are excluded.

Since the exact date of HIV infection is unknown, any assay data from blood draws 4 weeks prior to an infected participant's last seronegative sample and thereafter may be excluded. If an HIV-infected participant does not have a seronegative sample post enrollment, then all data from that participant may be excluded from the analysis.

Discrete categorical assay endpoints (eg, response rates) will be analyzed by tabulating the frequency of positive response for each assay by antigen and treatment arm at each timepoint for which an assessment is performed. Crude response rates will be presented with their corresponding 95% confidence interval estimates calculated using the score test method [1]. Because of the small numbers of control participants in each group, no adjustment will be made to the vaccine arm estimates for the false positive rates in the control arms. Barnard or Fisher's exact tests will be used to compare the response rates across treatment groups, with a significant difference declared if the 2-sided p-value is \leq 0.05; however the primary analysis will prioritize the one-sample comparison of those response rates to zero due to the power considerations

discussed above. In general Barnard's is preferred since under most circumstances it is more powerful than Fisher's [2].

In addition to response rate estimates for each timepoint, the probability of observing at least 1 positive response by a given timepoint and the probability of observing more than 1 positive response by a given timepoint will be estimated, with corresponding confidence intervals, for each vaccine arm using maximum likelihood-based methods [3].

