For quantitative assay data (eg, magnitudes and magnitude-breadth AUCs from the neutralizing antibody multiplex assay), graphical and tabular summaries of the distributions by antigen, treatment arm, and timepoint will be made. For all primary and secondary immunogenicity endpoints, box plots and plots of estimated reverse cumulative distribution curves will be used for graphical display of all of the study arms. Typically, the results will be shown for each vaccine arm and for the set of control arms pooled into one group.

Some immunologic assays have underlying continuous or count-type readout that are dichotomized into responder/nonresponder categories (eg, nAb multiplex assay positivity). If treatment arm differences for these assays are best summarized by a mixture model, then Lachenbruch's test statistic [4] will be used to evaluate the composite null hypothesis of equal response rates in the 2 arms and equal response distributions among responders in the 2 such arms. This test statistic equals the square of a binomial Z-statistic for comparing the response rates plus the square of a Wilcoxon statistic for comparing the response distributions in the subgroup of responders. A permutation procedure is used to obtain a 2-sided p-value. For estimation, differences in response rates between arms will be estimated using the methods described above, and in the subgroup of positive responders, differences in location parameters between arms will be estimated using the methods described above.

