Based upon previous HVTN trials as well as experience conducting infant clinical trials in the study population, missing up to 25% of immunogenicity results for a specific assay is anticipated due to study participants terminating from the study early, problems in shipping specimens, or low cell viability of processed peripheral blood mononuclear cells (PBMCs). To achieve unbiased statistical estimation and inferences with standard methods applied in a complete-case manner (only including participants with observed data in the analysis), missing data need to be missing completely at random (MCAR). Following the most commonly used definition, MCAR assumes that the probability of an observation being missing does not depend on any participant characteristics (observed or unobserved). When missing data are minimal (specifically if no more than 20% of participants are missing any values), then standard complete-case methods will be used, because violations of the MCAR assumption will have little impact on the estimates and hypothesis tests.

If a substantial amount of immunogenicity data is missing for an endpoint (at least 1 value missing from more than 20% of participants), then using the methods that require the MCAR assumption may give misleading results. In this situation, analyses of the immunogenicity endpoints at a specific timepoint will be performed using parametric generalized linear models fit by maximum likelihood. These methods provide unbiased estimation and inferences under the parametric modeling assumptions and the assumption that the missing data are missing at random (MAR). MAR assumes that the probability of an observation being missing may depend upon the observed responses and upon observed covariates, but not upon any unobserved factors. Generalized linear models for response rates will use a binomial error distribution and for quantitative endpoints, a normal error distribution. For assessing repeated immunogenicity measurement, linear mixed effects models will be used. If the immunological outcomes are left-and/or right- censored, then the linear mixed effects models of Hughes [5] will be used, because they accommodate the censoring. In addition, secondary analyses of repeated immunogenicity measurements may be done using weighted GEE [6] methods, which are valid under MAR. All

the models described above in this paragraph will include as covariates all available baseline predictors of the missing outcomes.

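### B-cell positivity is cut at the 85th percentile of the trial's own placebos; if the general test against zero is applied to it, an inert vaccine passes about 82–88% of the time

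*SAP*

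**What the plan says.** SAP 9.5 ties BCP to the primary objective on B-cell lineages. For the threshold it states that "the 85th percentile of the proportion of cells in the subset was calculated, among all placebo recipients (C2+C4+C6+C8", for a given subset at visits 8 and 12. SAP 9.5.1 lists BCP response rates and B-cell frequencies by treatment group. Neither section names a statistical test, a percentile definition, or whether positive means > or >=.

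The general rule is in SAP 8.4.1, repeated in Protocol 6.4.4.1. Response rates are tabulated for each assay; "no adjustment will be made to the vaccine arm estimates for the false positive rates in the control arms"; and, on testing, "the primary analysis will prioritize the one-sample comparison of those response rates to zero". The same section also provides between-arm methods:
- "Barnard or Fisher's exact tests will be used to compare the response rates across treatment groups".
- "If treatment arm differences for these assays are best summarized by a mixture model, then Lachenbruch's test statistic [4] will be used".
- When more than 20% of participants have missing values, "analyses of the immunogenicity endpoints at a specific timepoint will be performed using parametric generalized linear models fit by maximum likelihood".

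Protocol 6.1.2 describes the test against zero for "IgG binding Ab responses for CH103-like CD4bs and V1V2 for comparisons versus zero using binomial exact tests with 5% type-I error rate". It names no B-cell test, yet it treats response as "defined for Primary Endpoint 2 as initiation of either the CD4bs or the V1V2 B cell lineage".

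**The concern.** A null of zero is sensible only where background positivity is close to zero. Protocol 6.1.2 argues this for antibody: maternal antibody should have waned below detection by one year. The argument does not carry over to a cut-off that places some placebos above it by definition. If vaccine and placebo infants have the same B-cell frequencies, some vaccinees will also lie above it.

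Other assays avoid this. BAMA and ADCP (SAP 9.3, 9.4) take their cut-offs from HVTN 115 baseline data at the 95th percentile, with multiple-of-median criteria added. PVMA (SAP 9.7) names vaccine-versus-placebo differences and ratios. BCP, which is part of primary endpoint 2, has a looser, internal cut-off and no named comparison. At stake is whether a positive BCP result reflects the vaccine or the cut-off.

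**Working it through.** **Inputs.** Protocol 6.1.2 plans on 13 evaluable infants in pooled Groups 3 and 5 (18 × 0.75 = 13.5) and 8 placebos (10 × 0.75 = 7.5). I take m = 8 to 10 placebos, from the planning figure to full data. SAP section 8 names SAS and R, so both default percentiles are used. The null case is an inert vaccine, with vaccinee and placebo values exchangeable, for one subset at one visit.

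**1. The plan's own figure.** Protocol 6.1.2 claims more than 90% power with n = 13 at a true rate of 30%. With a null of zero, any responder rejects, so power is 1 − 0.7^13 = 99.0%. The claim holds. Table 6-3 agrees: the interval for 1/13 is 1.4 to 33.3% and excludes zero.

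**2. Placebos above the cut-off, untied values.**
- SAS default: order statistic ceil(0.85m) = 7, 8, 9 for m = 8, 9, 10. This is the second-largest placebo each time, so 1 is positive under > and 2 under >=.
- R default: position 1 + 0.85(m − 1) = 6.95, 7.80, 8.65. This lies between the third- and second-largest, so 2 are positive under either inequality.
- Range: 1/10 = 10% to 2/8 = 25%.

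**3. Chance that an inert vaccine gives at least 1 responder in 13.**
- SAS default: it fails to do so only if the top two of all m + 13 values are both placebos. The chance is therefore 1 − m(m − 1)/[(m + 13)(m + 12)]: 1 − 56/420 = 86.7% (m = 8), 1 − 72/462 = 84.4% (m = 9), 1 − 90/506 = 82.2% (m = 10).
- R default, 200,000 simulated trials per setting: about 86–88%, varying slightly with the shape of the distribution.
- Reference: with a known true 85th percentile, 1 − 0.85^13 = 87.9%.
- Expected response rate of the inert vaccine, SAS default: 2/(m + 1) = 22.2%, 20.0%, 18.2%. R default: 20–23%.
- Non-default definitions give less: 74.8–81.4% (median-unbiased) and 69.1–77.4% (Weibull).

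**4. Tied zeros (zeros mixed into lognormal data, R or SAS default).** Under >: 82–87% at 70% zeros, 69–71% at 90%, about 48% at 95%. Under >= at 90% zeros: 88–92%.

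**5. Discrimination.** At 13 v 8 (R default), the test against zero rejects 87% of the time with no effect and more than 99% of the time with a 1 SD shift.

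**6. Between-arm tests at 13 v 8 (simulated, normal data).** Barnard needs 8 of 13 responders when 1 placebo is positive, and 10 of 13 when 2 are.

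| Test | No effect | All shifted 1.0 SD | All shifted 1.4 SD | 30–40% shifted 3–10 SD |
|---|---|---|---|---|
| Barnard, SAS default, > | 3.7% | 48% | 73% | 22–39% |
| Barnard, R default | 0.7% | 24% | 48% | 5–11% |
| Exact rank-sum on frequency | 4.5% | 51% | 80% | 17–30% |

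The last column follows the 30–40% adult lineage-initiation rates in Protocol 6.1.2. The documents give no B-cell SD, so all shift sizes are assumptions.

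**The case against.** **The test may not be meant for BCP.** SAP 9.5 names no test. The priority clause appeals to power considerations, which the SAP does not contain; they are in Protocol 6.1.2, where the test is written for IgG binding antibody. This stands in part. A reader might infer that the plan instructs a test against zero for BCP, and the documents do not say that. It is the default reading, because SAP 8.4.1 covers each assay and exempts none.

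**The endpoint is quantification.** Protocol 5.1 defines the B-cell endpoint as quantification and phenotyping. Frequencies and response rates are shown by arm, so the placebo background should be visible. Protocol 6.1.2 calls the aim preliminary estimation, and no decision rule hangs on a BCP p-value. All of this stands and lowers the stakes.

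**Between-arm methods exist.** A reader might infer that none is planned. That is wrong: Barnard or Fisher, Lachenbruch and generalized linear models are all in SAP 8.4.1. At 13 of 18 and 8 of 10 evaluable, 7 of 28 infants (25%) are missing, above the 20% trigger, so the model clause would apply. However, it names no contrast and does not withdraw the priority given to zero. Barnard or Fisher ranks below the test against zero, and Lachenbruch is conditional on a mixture model fitting.

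**A rank-sum test is not always better.** This stands. With 30–40% responders, Barnard under the SAS default has more power.

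**Conclusion.** The point holds as a conditional one. The cut-off builds in a 10–25% placebo response rate, and the general rule, if applied to BCP, tests against a null that this cut-off makes false. An inert vaccine then passes about 82–88% of the time per subset and visit. That rests on 13 vaccinees, 8–10 placebos, untied values and the R or SAS default percentile. With many tied zeros the rate runs from about 48% (95% zeros, >) to 92% (90% zeros, >=), and the documents do not say how many zeros to expect.

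The documents do not support the stronger conclusion that the primary B-cell result must be decided this way. They leave open which analysis leads. Barnard's test on the calls is valid, but its power at 13 v 8 and 1 SD is 48% or 24% depending on a percentile rule that is not stated. This is a clarification that should be made.

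**What to change.** 1. State in SAP 9.5 that the test against zero does not apply to BCP, and reconcile SAP 8.4.1 and Protocol 6.4.4.1, which carry the same priority sentence.
2. Make the prioritized BCP analysis a between-arm comparison, T3+T5 versus pooled placebo, at visits 8 and 12. Because the endpoint is quantification, report the difference in B-cell frequency with a 95% CI, for example Hodges-Lehmann with a rank-sum test. Say how this fits the model clause when more than 20% of participants have missing values.
3. Keep Barnard on the calls as the responder comparison. State the percentile rule and the inequality that were used. SAP 9.5 is written in the past tense and the cut-off needs treatment codes, so it may be too late to fix the rule before unblinding.
4. Show the placebo rate and the built-in background beside every BCP response rate.

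**Cost:** wording in two documents and one extra table. The frequencies are already tabulated by arm, so no new data are needed. Power at 13 v 8 is modest (80% for rank-sum only at a common 1.4 SD shift), so the interval will tell the reader more than the p-value.
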